## 6.1. Methodology / Study Visits

### 6.1.1. Data Requirements per Visit with Visit window ( $\pm$ days)

The data requirements for each visit are shown in Table 4.

**Table 4**

Procedures/ Data (Y/N)	Visit 1	Visit 2	Visit 3/Study Exit	Unscheduled / Adverse Events
	BL	(1M from BL)	(3M from BL)	
Visit Window	N/A	$\pm$ 7 days	$\pm$ 14 days	N/A
Informed Consent	Y	N	N	N
Meet Inclusion/Exclusion Criteria	Y	N	N	N
Ocular and Medical History, Medications, Demographics	Y	N	N	N
Updated History, Symptoms and Problems	N	Y	Y	Y
Vision Tests (Visual Acuity)	Y	Y	Y	Y
Symptom Survey	Y	Y	Y	*
Nutrition Questionnaire	Y	N	Y	N
Comfort Questionnaires	Y	Y	Y	*
Health and Wellbeing Questionnaire	N	Y	Y	*
Body Mass Index and Body Fat Composition	Y	N	N	N
Tear Film Evaluation	Y	Y	Y	*
Slit-Lamp Biomicroscopy: Anterior ocular health including evaluation of cornea & conjunctiva	Y	Y	Y	Y
Dispense Study Product	Y	Y	N	N
Return Unused Study Product	N	Y	Y	*
Adverse Event Data	(Y)**	(Y)**	(Y)**	Y

Y = Yes, required information, N = No, not required

\* At optometrists discretion

\*\* If adverse event detected at time of visit

M = Month

### 6.1.2. Randomisation and Masking

Prior to initiation of study treatment, each subject who provides informed consent will be assigned to a subject number that will serve as the subject identification number on all study documents. Subject numbers will be assigned in ascending order and should not be omitted or reused.

Eligible subjects will be stratified according to dry eye severity (mild, moderate or severe) and then randomly assigned to 1 of the 2 study treatments. A randomization scheme will be prepared in advance.

Test and placebo capsules will be manufactured in accordance with local regulations including the TGA guidelines. All capsules will be identical in appearance as the outer capsule will be the same as the commercial test product. The manufacturer will code, bottle and label the test and placebo capsules to ensure that participants and investigators will be masked throughout the study duration. Both test and placebo capsules will have the same outer packaging and will be labelled as capsule "A" or "B". The code will be broken after completion of the study and data analysis, or if required for participant safety.

The recommended dosage will be 3 capsules per day by mouth to be taken with a meal for 40 days, and then 2 capsules per day thereafter for approximately 50 days, as per the manufacturer's guidelines.

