#### 10.2.2. Accountability

A Product Tracking spreadsheet is used for keeping track of who, where and when study product have been issued or dispensed to.

- **Receipt of Study Product:** Once invoice has been checked, the study product will be entered into the Study Product Tracking spreadsheet.
- **Issue of Study Product to Clinical Trial Participants:** The Optometrist is responsible for documenting the dispensing of the study product on the participant case record form.
- **Disposal of Unused Supplies:** Instruction will be obtained from the sponsor as to how to handle returned, unused study product.

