## 10.4. Participant Instructions

### General instructions to all participants

- Contact the clinic immediately if problems are experienced or if they have any questions or concerns
- Ingest the study product daily as per manufacturer's recommendation
- Return the unused study product at each follow-up visit
- Store the study product at room temperature and keep out of reach of children
- Continue to use any artificial tear supplements at the same frequency throughout the study, as used prior to the study
- Do not make any substantial changes to your intake of fish/diet for the duration of the study, unless instructed to do so for health/medical reasons. If so, please advise the study investigator as soon as possible.

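### Product is labelled only A or B for two arms, so one safety code-break could let informed staff infer the other allocations (low severity, cheap to improve)

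*Combined protocol and SAP*

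**What the plan says.** Section 6.1.2 has eligible subjects stratified by severity and then "randomly assigned to 1 of the 2 study treatments". The manufacturer does the coding, bottling and labelling, "to ensure that participants and investigators will be masked throughout the study duration". On the label: "Both test and placebo capsules will have the same outer packaging and will be labelled as capsule 'A' or 'B". On unmasking: "The code will be broken after completion of the study and data analysis, or if required for participant safety".

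Table 4 (section 6.1.1) schedules "Dispense Study Product" at Visits 1 and 2 and "Return Unused Study Product" at Visits 2 and 3. Section 10.4 instructs participants accordingly: "Return the unused study product at each follow-up visit". Section 10.2.2 adds: "The Optometrist is responsible for documenting the dispensing of the study product on the participant case record form".

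Section 8 numbers participants sequentially from 001. That number identifies a person; it is not described as a product code. Sections 10 (treatment and accountability), 12 (safety) and 13 (statistics) mention no kit number, bottle number or individual code-break record.

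**The concern.** As described, each arm has a single letter and there is one code to break. A safety break for one participant is meant to disclose one allocation. Under this labelling it discloses what both letters mean, so it also decodes every other bottle for anyone who sees the letters.

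At stake is the statement in section 6.1.2 that investigators stay masked for the whole study. Only assessments and decisions made after a break, by staff who learn its result, are exposed:

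- Redness and staining are graded by an observer (section 11.2, Appendices III and IV) and are primary safety variables in the synopsis.
- Some tear tests have an operator step. The phenol red thread is read in millimetres, and the investigator may end a break-up-time recording by asking for a blink (section 11.2).
- Withdrawal can rest on the investigator's opinion (section 7.2), and permanent discontinuation on the optometrist's (section 12.5).

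**Working it through.** The plan gives no figure on unmasking to reproduce. The check is a count, with a reading of who handles the product.

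**Inputs.** Participants: 69 per group × 2 = 138 (section 13.1.1). Treatments: 2. Letters: 2 (both section 6.1.2). Product handling: Table 4.

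1. **What one break decodes.** Letters per arm = 2 / 2 = 1. If one participant's letter is found to be supplement, the other letter must be placebo, and the reverse.
2. **How many others can be inferred.** 138 − 1 = 137. This ceiling does not depend on when the break occurs. If k participants have been dispensed product by then, the others are the k − 1 already enrolled and the 138 − k still to come, whose bottles would carry the same letters: (k − 1) + (138 − k) = 137. Timing affects only how many assessments remain to be influenced.
3. **With individual codes.** A break discloses 1 allocation, so 1 − 1 = 0 others.
4. **With more letters per arm.** Assuming equal use, four letters leave 138/4 − 1 = 33.5 others sharing the decoded letter, and ten leave 138/10 − 1 = 12.8. More letters reduce the problem without removing it.
5. **Could staff know the letters?** Per participant there are 2 dispensings and 2 returns, so 2 + 2 = 4 handlings of labelled product, spread over all 3 scheduled visits. The optometrist documents dispensing (section 10.2.2), examines the eye when a problem is reported (section 12.2) and judges permanent discontinuation (section 12.5). No section available for review separates dispensing from assessment or keeps the result of a break from assessors.

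The count is of allocations that could be inferred. It measures neither bias in any outcome nor the chance of a break.

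**The case against.** The strongest reply is that harm needs four things together: a break takes place, assessing staff learn its result, they know other participants' letters, and assessments are still to come. The documents do not say that any of these will happen.

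A break may seldom be needed. Section 4.2.1 answers untoward signs by stopping the product, and section 12.5 rests permanent discontinuation on clinical opinion. Neither step requires knowledge of the allocation. The foreseeable product risks in section 12.4.1 are stomach pain (<2%) and diarrhoea (<1%). All of this stands and keeps the severity low. It does not remove the weakness, because section 6.1.2 itself provides for a break on safety grounds.

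It is also fair that sections 2 and 3 (Investigator(s), Medical Expert) were not in the text available for review and may set out staff roles, and that section 11.2 does not name who grades at scheduled visits. The manufacturer may use a further code that is not written down. The point is therefore about the scheme as described.

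A reader might infer more than this, and the documents do not support it:

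- *Masking will fail.* No code-break rate is given, so no probability can be stated.
- *The primary endpoint is compromised.* It is self-reported on paper questionnaires (sections 6.1.6 and 9.1), and participants need not learn of a break. It is less exposed rather than immune, since the OSDI form in Appendix II is worded for someone putting the questions to the patient.
- *Allocation concealment is defective.* The labelling alone does not show this; section 6.1.2 has the randomisation scheme prepared in advance.

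**Conclusion.** The point holds as a low-severity improvement. With the labelling described, one safety break could let informed staff infer up to the other 137 allocations, against 0 with individual codes.

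This assumes that the letter is the whole product code, that the staff concerned learn the result of the break, and that they know other participants' letters. The figure of 137 is a ceiling. The likelihood is unknown and probably low, and the exposure is confined to later observer-graded signs, operator-dependent tests and discretionary withdrawals. Sample size and endpoints are unaffected.

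**What to change.** **Section 6.1.2.** Keep identical outer packaging and replace the A/B label with wording such as:

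> Each participant's bottles carry a unique kit number, and product dispensed at Visit 2 carries the same number. One code-break record is held per kit, so that a break reveals that participant's allocation only.

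**Section 10.2.2.** Record the kit number at each dispensing.

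**Analysis datasets.** If A and B are used as group labels for the final analysis or for the interim analysis that section 13.1 allows, withhold those datasets until the database is final from site staff who dispense, assess or learn of a break. Section 14.3 makes data accessible to study personnel, so without this limit an A/B dataset would allow the same inference.

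**Cost.** The manufacturer already codes and labels the product. The additions are a numbered label run, 138 code-break records plus one for each spare kit, some spare kits because the stratum sizes in section 6.1.3 are targets, a kit-number field in the dispensing record, and matching of kit to participant at Visit 2. The documents give no basis for the number of spares. If individual codes already exist, writing them into these two sections settles the labelling point at almost no cost. When a code may be broken is unchanged.

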### 6.1.3. Clinical Trial Population

A total of 138 participants will be recruited for the study, which includes allowance for a 10% drop-out rate).

This sample size was calculated on the basis of detecting a difference in Ocular Surface Disease Index (OSDI) score of 10, with a standard deviation of 20, assuming an estimate of type 1 error  $\alpha = 0.05$  and power of 80% for a two tailed test. These values were obtained from Schiffman et. al. who demonstrated a mean difference in OSDI score of 10 between normal subjects and those with mild to moderate dry eye, with a standard deviation of up to 20.

Every effort will be made to stratify enrolment by disease severity to ensure participants with mild, moderate and severe dry eye are represented in the study population. Stratification will be in a 2:2:1 fashion i.e. OSDI score >12 (55 participants), OSDI score >20 (55 participants) and OSDI score >45 (28 participants).

Trial participants will be recruited from the local population at the investigational site. An e-mail invitation will be circulated to all SOVS staff, the Brien Holden Vision Institute, the Centre for Eye Health, SOVS post-graduate students, UNSW administrative staff and previous study participants who have indicated their willingness to be contacted to participate in future research studies. Advertisements may also be posted in University newsletters, notice boards, websites, local newspapers, social media (e.g. Facebook), on the SOVS clinic TV screen and other local advertising and community websites.

#### 6.1.4. Trial Duration

This is a 3 month dispensing study. Participants will attend a total of 3 scheduled visits at Baseline, 1 month and 3 months.

**Table 5: Visits**

Visit Type:	Abbreviation
Baseline	BL
1 month	1M
3 months	3M

For the purpose of these studies, 1 month will be considered the same as 30 days.

### **6.1.5. Enrolment**

A study participant is considered enrolled when they have signed the Participant Information Statement and Consent Form.

### **6.1.6. Primary Endpoint**

Subjective ocular comfort and symptoms assessed using validated questionnaires.

### **6.1.7. Secondary Endpoint(s)**

Non-invasive tear film break-up time, tear evaporation rate, tear meniscus height, tear volume and lipid layer thickness.

## 7. SELECTION AND WITHDRAWAL OF PARTICIPANTS

### 7.1. Participant Selection

One hundred and thirty-eight (138) participants, both male and female, age 18 years and upwards who experience symptoms of ocular dryness will be enrolled into the study.

Every effort will be made to stratify enrolment by disease severity to ensure participants with mild, moderate and severe dry eye are represented in the study population. Stratification will be in a 2:2:1 fashion i.e. OSDI score >12 (55 participants), OSDI score >20 (55 participants) and OSDI score >45 (28 participants).

Informed consent will be obtained prior to any clinical trial procedures.

All participants will conform to the clinical trial entry criteria listed below:

#### 7.1.1. Inclusion Criteria

- Able to read and comprehend English and give informed consent as demonstrated by signing a record of informed consent;
- Be at least 18 years old;
- Have symptoms of ocular discomfort as measured with the Ocular Surface Disease Index (OSDI) score of >12 at the Baseline visit;
- Willing to comply with the dosage and study visit schedule as directed by the investigator;
- No contact lens wear in the last 30 days and willing to refrain from contact lens wear for the duration of the study;
- No planned changes to diet and willing not to substantially alter their usual diet for the duration of the study, including their typical intake of fish;
- Willingness to notify the study investigator if instructed to alter their diet by health/medical practitioner;
- Willing to continue using any artificial tear supplements at the same frequency throughout the study, as used prior to the study;
- Have health and ocular health findings which would not prevent the participant from safely ingesting dietary supplementation with combination omega oils.

#### 7.1.2. Exclusion Criteria

- Any systemic disease that would preclude participants from safely ingesting dietary supplementation with combination omega oils;
- Self-reported allergy/sensitivity to any of the study product ingredients;
- Use of any polyunsaturated fatty acid-containing dietary supplements (such as fish oil, evening primrose oil, linseed oil) up to 12 weeks prior to start of the study;

- Use of any of the following medications (including steroids) up to 12 weeks prior to the start of the study or during the course of the study:
  - Ocular medication, category S3 and above;
  - Any systemic or topical medications that will affect ocular physiology e.g. anti-acne medications such as Roaccutane and corticosteroid or immunosuppressant medications such as Hydrocortisone, Prednisolone and antihistamine medications such as Claritine;
- Any systemic disease that may affect ocular health e.g. Graves disease, and auto-immune diseases such as ankylosing spondylitis, multiple sclerosis and systemic lupus erythematosus;
- Epilepsy or history of migraines exacerbated by flashing, strobe-like lights;
- Eye surgery within 6 months immediately prior to enrolment for this study;
- Rigid or soft contact lens wearer, including orthokeratology in the last 30 days;
- Previous corneal refractive surgery;
- Pregnancy or breastfeeding.
- The Investigator may, at his/her discretion, exclude anyone else who they believe may not be able to fulfil the study requirements, or if it is believed to be in the participant's best interests.

## **7.2. Participant Withdrawal**

Participants may be permanently discontinued from the clinical trial for any of the following reasons:

- If, in the Investigator's opinion, it is in the best interest of the participant;
- Persistent clinical trial-related symptoms/complaints that are not correctable;
- Has a serious adverse event/serious adverse device event that is eye/lens/solution related and/or which, in the Investigator's or Sponsor's opinion, requires withdrawal of the participant;
- Participant voluntarily withdraws consent from the clinical trial (i.e. Revocation of Consent);
- Participant is lost to follow-up, or relocates and cannot attend the clinic;
- If a participant is not compliant with the clinical trial requirements and instructions e.g. visit schedule;
- Repeated protocol violations/deviations.

## **7.3. Withdrawal and Follow-up Procedure**

Participants who are permanently withdrawn from the study should be seen as soon as possible after stopping use of the study product for a final visit to assess participant safety and to return any unused study product. This may be done at a routine clinic visit or an unscheduled visit if it occurs between routinely scheduled visits.

### 7.3.1. The Final Study Exit Visit

Where possible, the data requirements for the final study exit visit are the same assessments as for the 3 month visit shown in Table 5. However, the minimum data requirements include:

- Visual acuity
- Slit-lamp biomicroscopy (ocular redness, corneal and conjunctival staining)

For withdrawal of consent, a 'Revocation of Consent' document should also be signed, if possible.

### 7.3.2. Lost to Follow-up

A participant will be considered lost to follow-up, after three documented and failed attempts have been made to contact the participant – two phone calls and one written. Any contact should attempt to gain the following information:

- reason participant has not returned to clinic
- safety (previous/new adverse events status), and
- concomitant therapies.

### 7.3.3. Event Follow-up

If a participant has experienced an adverse event that is continuing at the end of the study participation, the event is marked as ongoing. The Investigator should ensure appropriate follow-up care is arranged/provided to the participant as appropriate.

If an adverse device event, or a serious adverse event/serious adverse device event has occurred and is continuing, the participant should be followed until the event has resolved, or stabilised if there is no chance of improvement. Source notes and the reporting form should be updated as appropriate, and the information forwarded to the Sponsor/HREC/TGA as necessary.

### 7.3.4. Whether and How Participants are to be Replaced:

Participants who experience an adverse response during the course of the study, that requires early discontinuation from the study, will not be replaced. Participants who are not suitable at Baseline will be replaced, until the enrolment target is reached.

## **7.4. Early Termination of Trial**

The trial may be stopped early for any one or more of the following reasons:

- If the monitoring of the clinical trial reveals unacceptable levels of device-related adverse events, even though some of the participants may not be affected;
- If the Investigator does not adhere to the protocol;
- If the Sponsor decides to stop the study for any reason, with appropriate notification.

In the event of early termination of the trial, the HREC will be notified.

## 8. NUMBERING

Participant numbering will occur sequentially commencing with '001'.

## 9. EQUIPMENT TO BE USED / STANDARD & NON-STANDARD PRACTICE PROCEDURES

### 9.1. Standard Equipment and Procedures:

- **Visual Acuity:** Measurement of the standard of vision achieved with spectacles or contact lenses using standard letter charts. Measurements are taken under monocular and/or binocular conditions.
- **Slit-Lamp Biomicroscopy:** A specialised microscope with its own light source is used to examine the anterior eye.
- **Corneal and Conjunctival Staining:** The corneal surface is assessed by instilling a harmless fluorescent dye called 'fluorescein' using a sterile fluorescein strip moistened with saline. The eye is assessed with the slit-lamp biomicroscope using a cobalt blue filtered light and a Wratten 12 filter. The conjunctival surface is assessed by instilling a harmless dye called 'lissamine green' using a sterile lissamine green strip moistened with saline. The eye is assessed using the slit-lamp biomicroscope and white light.
- **Questionnaires:** Questions assessing eye symptoms, diet, product usage and general health and wellbeing will be administered on paper forms.
- **LipiView® Ocular Surface Interferometer (TearScience®):** Will be used to measure the absolute thickness of the tear film lipid layer. The participant's eye is positioned in front of an illumination source that is directed toward the tear film on the corneal surface. The camera records a 20-second video of the tear film interference and subsequently displays a value in interferometric colour units (ICU), where 1 ICU approximates 1nm of lipid layer thickness.
- **Phenol red thread test:** Will be used to measure tear volume.
- **Participant History File:** Created at commencement of study and maintained throughout the trial. Contains relevant references to participant's medical history (both prior to participation in the trial and ongoing throughout the trial); and contains details of any problems encountered during the trial (either through observation by the investigator or as volunteered by the participant).

## 9.2. *Non-Standard Equipment and Procedures:*

Non-standard procedures that may be performed include:

- ***Tear Evaporation Rate:*** The Vapometer is a closed chamber device which is used for measuring transepidermal water loss. Participants will be seated upright on a chair and provided with a distance fixation target. To minimize the effect of skin evaporation, petroleum jelly (Vaseline\_, <http://www.unilever.com.au/brands-in-action/detail/Vaseline/299339/>) will be applied over the upper eyelid and the surrounding areas. The VapoMeter will then be placed over the eye and a non-invasive measurement of tear evaporation will be taken within 10 seconds. Participants will be instructed not to blink during open eye measurement and to maintain a normal straight gaze at the fixation target. Evaporation rates with the eyes closed will also be taken, in order to account for the skin evaporation from eyelids and surrounding skin tissue.
- ***Oculus Keratograph 5M (Oculus®):*** Will be used to measure non-invasive tear break-up time and tear meniscus height. The participant's eye is positioned in front of a placido disc illumination which allows detection of the tear film and tear prism non-invasively. The associated software measures non-invasive tear break-up time and tear meniscus height.
- ***Photography/Video:*** A photograph of the eye will be taken, and photographic/video recording of any interesting/unusual findings may also be made for documentation and/or follow-up purposes.
- ***Body Mass Index (weight/height):*** Will be measured using a digital scale (Charder Scale MS 3400; Charder Electronic Co. Ltd., Taichung City, Taiwan).
- ***Body Fat Composition:*** Will be measured using a Tanita monitor. This is a non-invasive procedure that uses bioelectrical impedance analysis and sends a very low, safe electrical signal from four metal electrodes through the participant's feet to measure body fat composition (Tanita BC-601, Tanita, Australia).

